### Stress induced craving paradigm

The pathophysiology of nicotine dependence includes the interaction between stress, environment and body physiology. Multiple previous studies have modeled craving for nicotine in the presence of stress, to approximate real world scenarios. Before we test TBS as a clinical intervention, we will explore whether one session of TBS can modulate craving in the context of induced stress. Two promising paradigms for stress induction are the cold pressor test (CPT) wherein participants immerse their feet in ice cold water (2-4

degree Celsius) for three minutes and the paced serial addition task (PASAT). The cold pressor test invokes an immediate cardiovascular stress response, initiated by the sympathetic nervous system, followed by a neuroendocrine response controlled by the hypothalamus-pituitary-adrenal (HPA) axis. The PASAT is a cognitively challenging task and will be performed in parallel with the CPT as an additional means for stress induction. The task requires participants to listen to a standardized audio-recording of a series of single-digit numbers and to say aloud the sum of the last two numbers presented (within each inter-trial interval). The PASAT will also last about three minutes. Peak stress response occurred 20 minutes after these paradigms were performed. In our pilot study, these paradigms will be performed simultaneously, and followed by the tobacco craving questionnaire (TCQ).

#### The Tobacco Craving Questionnaire-short form (TCQ-SF)

It consists of 12 items rated on a visual analogue scale. The original Tobacco Craving Questionnaire (TCQ) is a valid and reliable 47-item self-report instrument that assesses tobacco craving in four dimensions: emotionality, expectancy, compulsivity, and purposefulness. The short form has been found to be as valid and reliable as the original version.

#### Attentional Bias task

We will measure attentional bias using a validated database of smoking and neutral cues and Tobii Pro Fusion 120 Hz eye tracker (Tobii Technology, Sweden). Smoking and neutral cues will be presented side-by-side on the screen for 1000?milliseconds. Eye tracking will record eye movements and fixation times for both cue types. Upon offset of the cues, a visual probe ('X') will appear on either the left or right side of the computer screen. Participants will be instructed to respond as quickly as possible to the probe. The primary dependent variable will be mean fixation time (milliseconds) calculated by summing the total fixation time for each cue type and then dividing by the total number of critical trials (i.e., 40). Reaction times to the visual probe will also be collected.

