**SUBJECT DEMOGRAPHICS**

0 unresolved comment(s)

Age level of human subjects: (i.e., 6 mths.; 2yrs., etc.)  to **Study Population:**

Describe the characteristics of the subject population, including age range, gender, ethnic background and health status. Identify the criteria for inclusion and exclusion.

Provide the following information:

- A description of the subject selection criteria and rationale for selection in terms of the scientific objectives and proposed study design;
- A compelling rationale for proposed exclusion of any sex/gender or racial/ethnic group;
- Justification for the inclusion of vulnerable groups such as children, prisoners, adults with impaired consent capacity, or others who may be vulnerable to coercion or undue influence.

Please consider this [FDA Guidance on Enrollment of Participants from Underrepresented Populations in Clinical Studies](#)

Inclusion criteria. Potential participants will be: 1) Patients enrolled in the Bluegrass Clinic; 2) 18-60 years of age; 3) male or female gender 4) Able to read, understand and communicate in English; 5) willing to adhere to the general rules of the Bluegrass Clinic/SMARTClinic/Beyond Birth Clinic; 6) willing and able to abstain from drug use other than Suboxone; 7) exhaled breath on day of study CO < 5 ppm; 8) Stabilized on maintenance buprenorphine if having comorbid opioid use disorder.

Exclusion criteria. Positive pregnancy test for females, traumatic brain injury, history of seizure disorder, history of or current diagnosis of schizophrenia, intracranial metal shrapnel, previous adverse effect with TMS, sub-threshold consistency while performing behavioral tasks, failure to show baseline attentional bias to smoking versus neutral cues.

The main study is not connected to the Bluegrass HIV clinic, SMART clinic or the Beyond Birth Clinic. A person can be enrolled and receiving care at these clinics, and their participation in the research project does not impact their standing in any of these clinics. Participation is truly voluntary in nature.

To modify: A new updated phone script will be attached to this section.

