## Objectives

List your research objectives. Please include a summary of intended research objectives in the box below.

To demonstrate whether four sessions of TBS improves attentional bias and craving in PLWHA smokers compared to four sessions of sham stimulation. We hypothesize 4 sessions of TBS to the left DLPFC will significantly improve attentional bias and craving for smoking cues compared to neutral cues in a population of subjects who are smokers with HIV/AIDS compared to sham stimulation.

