## Study Design

Describe and explain the study design (e.g., observational, secondary analysis, single/double blind, parallel, crossover, deception, etc.).

- *Clinical Research:* Indicate whether subjects will be randomized and whether subjects will receive any placebo.

- **Community-Based Participatory Research:** If you are conducting [community-based participatory research \(CBPR\)](#), describe strategies for involvement of community members in the design and implementation of the study, and dissemination of results from the study.
- **Qualitative research:** Indicate ranges where flexibility is needed, if a fixed interview transcript is not available, describe interview topics including the most sensitive potential questions.
- **Research Repositories:** If the purpose of this submission is to establish a Research Repository (bank, registry) and the material you plan to collect is already available from a commercial supplier, clinical lab, or established IRB approved research repository, provide scientific justification for establishing an additional repository collecting duplicate material. Describe the repository design and operating procedures. For relevant information to include, see the [UK Research Biospecimen Bank Guidance](#) or the [UK Research Registry Guidance](#).

This will be a crossover randomized controlled trial. Recruitment for the study will be done by research assistant and/or principal investigator. All subjects will receive both TBS and sham stimulation in a randomized manner with counterbalancing. Subjects will be randomized to two groups - one group that receives actual TBS first and sham TMS later, the other group receiving sham TMS first and TBS later. The PI ([name]) will be blind to the randomization status and will supervise the TMS session. The PI will remain blind to the randomization status. Subjects will also remain blind to the randomization status. This will be facilitated by the Magventure Active/sham TMS coil which has been shown to maintain integrity of blinding in subjects regarding group assignment. We will recruit 30 subjects in each arm (2 arms – TBS and sham, total n=60), subjects will be randomized to one of these arms using a computer-generated randomization protocol.

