**Eye Tracker.** The Tobii Pro Fusion housed at [name] is an exceptionally flexible remote eye tracking system offering supreme tracking performance in a wide array of human behavior research studies. This small eye tracking research system offers unprecedented portability and freedom of head movement in combination with unparalleled tracking accuracy and robust participant tracking capability. It allows for both screen and real-world test scenarios. For screen based research, it can be used with a laptop, an external monitor or an all-in-one PC. It can be mounted below most screens. With the eye tracker flush mounted on a screen, researchers can achieve highly accurate results for stimuli presentation on screens. Using a desk stand, one can track larger screens. This gives researchers the freedom to present stimuli on a screen that best meets the specific needs of the study at hand. The eye tracking system captures data up to speeds of 250 Hz (available 60, 120, 250 Hz modes). It delivers unparalleled data accuracy within the whole tracking box and very robust participant tracking capability. Robust eye tracking capability ensures very low data loss in real life conditions. The system with automatic selection of bright or dark pupil eye tracking accommodates for large variations in experimental conditions and demographic populations. The system also comes fitted with Tobii Pro Lab. This is a versatile biometric software platform designed for extensive research into human behavior using eye tracking analysis. It also has added ability to be combined with other physiological data streams. From in-store shopper research to psychology experiments, Pro Lab makes it easy for anyone to start using various biometric tools in their research in order to further expand the scope and richness of their insights. Pro Lab works well with both screen-based and wearable eye trackers.

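### The primary fixation-time variable is divided by a fixed 40 trials with no rule for lost gaze, so gaze loss biases the per-cue means directly and the smoking-versus-neutral difference in proportion to the true bias

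*Combined protocol and SAP*

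**What the plan says.** Under Research Procedures, the Attentional Bias task section shows one smoking and one neutral cue together on every trial: "Smoking and neutral cues will be presented side-by-side on the screen". It then names the outcome: "The primary dependent variable will be mean fixation time (milliseconds"). The same sentence goes on to give the formula, under which the outcome is "calculated by summing the total fixation time for each cue type and then dividing by the total number of critical trials (i.e., 40"). This gives two numbers per assessment, one for each cue type. No difference or proportion score is defined.

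Two other sections treat the quantity as a contrast. The Objectives hypothesise that TBS "will significantly improve attentional bias and craving for smoking cues compared to neutral cues", relative to sham. The exclusion criteria under Subject Demographics include "failure to show baseline attentional bias to smoking versus neutral cues", with no size or cut-off.

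No section gives a gaze-validity threshold, a rule for dropping trials, an adjusted denominator or a minimum number of usable trials. The nearest text is an exclusion for "sub-threshold consistency while performing behavioral tasks", which applies to subjects rather than trials and is not defined, and a sentence in the Eye Tracker description under Resources: "Robust eye tracking capability ensures very low data loss in real life conditions". That sentence gives no rate.

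**The concern.** A denominator fixed at the number of trials presented treats a trial without recorded gaze as a trial on which the subject looked at neither cue. These are different events. The first is missing data and the second is a genuine observation of zero.

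Two consequences follow. If more gaze is lost under one condition than the other, the recorded fixation time falls under that condition whether or not stimulation did anything. If loss is equal, there is no spurious difference between conditions, but every difference score is pulled towards zero, including the one used to judge baseline bias.

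How much this matters depends on which number is compared between TBS and sham. The plan leaves that open, because it defines the per-cue means while its hypothesis concerns their contrast.

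**Working it through.** The documents give no expected fixation time, SD, loss rate or power figure for this outcome, so there is no plan figure to reproduce. The check evaluates the plan's formula directly.

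**Inputs from the documents.** 40 critical trials; both cues on screen on each trial; a 1,000 ms display.

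**Assumed inputs.** True fixation per valid trial of 420 ms (smoking) and 370 ms (neutral), identical under TBS and sham. The bias is 50 ms, there is no treatment effect, and the sum of 790 ms fits within the display. Loss is 2 of 40 trials (5%) under sham and 6 of 40 (15%) under TBS. Whole trials are lost, independently of where the subject was looking.

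**Formula.** With true mean m and L lost trials, recorded mean = m × (40 − L)/40. One lost trial costs 1/40 = 2.5% of each cue mean.

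| Score | Sham, 5% lost | TBS, 15% lost | Spurious TBS − sham |
|---|---|---|---|
| Smoking mean | 420 × 0.95 = 399 | 420 × 0.85 = 357 | −42 ms |
| Neutral mean | 370 × 0.95 = 351.5 | 370 × 0.85 = 314.5 | −37 ms |
| Smoking − neutral | 47.5 | 42.5 | −5 ms |
| Smoking / (smoking + neutral) | 399/750.5 = 0.532 | 357/671.5 = 0.532 | 0 |

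The per-cue artefact is the whole cue mean times the difference in loss. The artefact on the difference score is only the true bias times that difference, because side-by-side presentation takes time from both cues. In a proportion score the loss factor cancels.

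**Range.** At 5% v 15% loss, assumed biases of 40 to 200 ms give 4 to 20 ms on the difference score. With a 100 ms bias and 5% v 25% loss it is 20 ms. With no bias it is zero. The sign reverses if the heavier loss falls under sham.

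**Equal loss.** There is no spurious TBS-minus-sham effect. The 50 ms difference score becomes 50 × 0.90 = 45 ms at 10% loss and 50 × 0.70 = 35 ms at 30%.

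**False positives on the difference score.** With the 5 ms artefact, an assumed SD of 80 ms and a two-sample test of 30 per arm, the noncentrality is 5/(80 × √(2/30)) = 0.24 and the rejection rate about 5.7% against a nominal 5%. For 5% v 10% loss (2.5 ms) it is 5.2%. For the 5 ms artefact and SDs of 40 to 113 ms the range is 7.6% down to 5.3%. A paired test in 60 subjects, with the same SDs applied to the within-subject change, gives 15.9% down to 6.3%.

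**Effect of the fix.** Dividing by the number of valid trials removes the factor (40 − L)/40, so the expected artefact is zero for each score. A simulation of 20,000 replicates (450 and 350 ms, 5% v 15% loss, heavier loss under sham) gave 9.4 ms on the difference score with the fixed 40 and −0.6 ms with the valid-trial count, against expected values of 10 and 0.

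**The case against.** The strongest reply is that the plan measures attentional bias, and that the Objectives and the entry criterion both frame it as smoking versus neutral. On that reading the per-cue means are only inputs to a contrast, and the contrast is largely protected. This stands, and it governs the size of the point. It does not remove the shrinkage under equal loss, and it relies on a score that the plan does not write down.

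The figure of 40 may also be just the nominal trial count, with invalid trials dropped in practice. The plan never says in words that lost trials score zero; that follows from using the formula as written. It is still the only scoring rule given.

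Thirdly, nothing in the documents indicates that loss differs between TBS and sham, or in which direction, and the only remark on loss calls it very low. That is fair, although the remark is a general equipment description without a figure.

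Three stronger readings are tempting but not supported:

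- **Any difference in tracking loss appears as a treatment effect.** This is true of a per-cue mean. It is not true of a proportion score, nor of a difference score when there is no bias.
- **The trial has a large false-positive rate.** That needs smoking-cue fixation alone to be tested between independent arms. No section specifies such a test, and although Study Design mentions 30 subjects per arm, it describes a crossover: "All subjects will receive both TBS and sham stimulation in a randomized manner with counterbalancing".
- **The scoring rule wrongly excludes subjects.** Proportional shrinkage does not change the sign of a bias, and the exclusion criterion gives no millisecond cut-off that a shrunken score could miss.

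**Conclusion.** The point holds as a scoring defect of moderate size. The primary variable has a fixed denominator and no lost-gaze rule, and it is defined per cue although the hypothesis concerns a contrast. At an assumed 5% v 15% loss the artefact is 42 ms on an assumed 420 ms cue mean, about 5 ms on an assumed 50 ms difference, and nil on a proportion.

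These figures rest on assumed means, SDs and loss rates, and on whole-trial loss unrelated to gaze position. If loss fell only on smoking-cue fixations, the difference score would be exposed too: with 400 ms on each cue and 2 v 6 trials affected, it moves by 400 × 4/40 = 40 ms. A valid-trial denominator cannot be relied on to correct loss of that kind.

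The Continuation Review section reports 4 subjects enrolled, enrolment closed and data under analysis. With so few, one subject's tracking matters. Four extra lost trials in one person under one condition move that condition's average smoking mean by 420 × (4/40)/4 = 10.5 ms and the average difference by 50 × (4/40)/4 = 1.25 ms.

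**What to change.** In the Attentional Bias task section:

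- Define the primary variable as the smoking-minus-neutral fixation difference per valid-gaze trial, or as smoking fixation divided by total cue fixation. Replace the fixed 40 with the number of valid-gaze trials.
- Define a valid trial by the amount of gaze recorded, not by whether a cue was fixated, so that a subject who really looked at neither cue keeps a true zero.
- Set a minimum number of valid trials for a score to count.
- Report valid-trial counts by condition, so that readers can see whether loss was unequal.
- Use the same score for the baseline-bias criterion under Subject Demographics. As enrolment is closed, this now means re-scoring and reporting baseline bias for the subjects already entered.

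The rules should be fixed before scores are compared by condition. The cost is one or two sentences of protocol text, a small change to the scoring script, and possibly a few scores lost below the minimum. No new data are needed, provided that the trial-level gaze recordings have been kept.

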#### Attention bias behavioral activation (ABBA) task using go/no go

A modified cued go/no-go task is used as a measure of inhibitory control. The procedures and parameters for the attentional bias-behavioral activation (ABBA) task are identical to the traditional cued go/no-go task except that opiate-related images serve as go cues and neutral images serve as no-go cues. Opiate related images and neutral images that will be used for this task are attached below.

#### Delayed discounting task

Participants are presented a fixed set of 27 choices between smaller, immediate rewards (SIRs) and larger, delayed rewards (LDRs). Three trials of the task are presented, money versus money, money versus opiate reward, and opiate versus opiate reward in varying amounts and with varying time periods. The 27 choices in each of these trial types define ten ranges of discount rates, eight of which are bounded above and below and two of which represent the endpoints (choices of all 27 immediate rewards or all 27 delayed rewards). Based on participants' choices of the immediate reward across trials, each participant is assigned a k value corresponding to the geometric midpoint of one of the eight ranges or one of the two endpoint values. Each participant is assigned a k value that yields the highest proportion of choices consistent with that assignment. That is, for each participant we compute the proportion of that person's choices that were consistent with assignment to each of the 10 values of k defined by the questionnaire (bounded or unbounded), and the participant is assigned to the value that yields the highest consistency among his or her choices. The discount rate that yields the highest relative consistency across trials provides the best estimate of the participant's k value. When two or more values yielded equal consistency, the participant is assigned a value corresponding to the geometric mean of those values. The discounting rate (k) is estimated with nonlinear regression using Mazur's (1987) hyperbolic-decay model,  $vd = V / (1+kd)$ , where V is the value of a an outcome delayed by d days and vd is the value of the immediate outcome – a proportion of V subjectively discounted at "rate" k. Distributions of k-values transformed with the natural logarithm (ln) tend to be approximately normal.

Barratt impulsiveness scale (BIS-11) - The BIS-11 is a 30-item self-report questionnaire to assess impulsivity that has been validated in multiple studies and other languages.

#### Modification Request to the research procedures:

An additional two follow-up visits will be added to this study research procedure by the study Principal Investigator [name]. [name]. The research team will follow up with subjects at one-week and two-week intervals with a urine cotinine test (ACCUTEST urine cotinine tests from Janet Pharmacocal) and carbon monoxide testing using Smokerlyzer (Bedfont Scientific Limited). These two follow-up short visits 2-3 minutes will be performed in the SMART clinic lab space. The CUTEST cotinine assay is a qualitative test and indicates the presence or absence of cotinine. Cotinine is a metabolite of nicotine, and these measures will help assess abstinence from cigarette smoking in response to our intervention. The additional follow-up visit details will be incorporated into the informed consent form and in the E-IRB application for IRB further review and approval.

#### Modification Request to the research procedures:

We will record resting heart rate 4 times on study day 2 using EKG leads. We will record at baseline, after the stress induction paradigm, after first TMS session and after the 4th session. This will allow us to monitor heart rate variability changes in response to stress and TMS.

We will also draw blood samples (2 ml each in EDTA) on study days 1 and 2 at the CCTS outpatient clinic situated on 3rd floor of PAV H, to measure high sensitivity C-reactive protein (CRP). This assay will assess inflammatory status. The assay will be done by [name] who has been added as a co-investigator to the protocol.

### Attachments

Attach Type	File Name
ResearchProcedures	(Figure 1) Timeline Tasks for four visits.docx
ResearchProcedures	[name] Email_Clean.docx
ResearchProcedures	TAQ.PNG
ResearchProcedures	BIS.pdf
ResearchProcedures	TCQ.png
ResearchProcedures	TMSSideEffects.doc

### Data Collection & Research Materials

In this section, please provide the following:

- Describe all sources or methods for obtaining research materials about or from living individuals (such as specimens, records, surveys, interviews, participant observation, etc.), and explain why this information is needed to conduct the study.
- For each source or method described, please list or attach all data to be collected (such as genetic information, interview scripts, survey tools, data collection forms for existing data, etc.).
- If you will conduct a record or chart review, list the beginning and end dates of the records you will view.

#### Motor Threshold

Eye tracking to measure attentional bias for smoking cues versus neutral cues

#### Delay discounting task

Attention bias behavioral activation (ABBA) task using go/no go

Barratt impulsiveness scale (BIS-11)

Tobacco Craving questionnaire (TCQ)

TMS Side effects scale

Treatment acceptability questionnaire (TAQ)

Resting state functional magnetic resonance imaging (fMRI)

Neuroimaging data will be acquired on a Siemens 3-Tesla (3T) PRISMA scanner. A high-resolution (1 cubic millimeter voxels) T1-weighted MP-RAGE structural image will be acquired for each subject. Functional images will be acquired using echo-planar imaging. Hyper-angulated volumes will be acquired with 37 ascending and interleaved slices at an angle 30-degrees to the anterior-posterior commissure to prevent OFC washout. Additional parameters will be similar to those used in other approved neuroimaging protocols in our lab (e.g., a repetition time (TR) of 2 seconds, echo time (TE) of 25 ms, a flip angle of 90 degrees, and functional voxels of size 3.4mm x 3.4mm x 4.0mm). Image preprocessing will be performed in statistical parametric mapping (SPM) 12 software using standard procedures (see [name] et al., 2014). Data from functional scans will be treated similarly to fMRI data in previous studies (e.g., slice-timing corrected, head-motion corrected, warped into MNI standard space, re-sliced to 4 cubic millimeter voxels and smoothed with an 8mm full-width, half-maximum (FWHM) Gaussian kernel).

To modify: An additional two follow-up visits will be added to this study research procedure by the study Principal Investigator [name]. [name]. The research team will follow up with subjects at one-week and two-week intervals with a urine cotinine test (ACCUTEST urine cotinine tests from Janet Pharmacocal) and carbon monoxide testing using Smokerlyzer (Bedfont Scientific Limited). These will be performed in the SMART clinic lab space. The CUTEST cotinine assay is a qualitative test and indicates the presence or absence of cotinine. Cotinine is a metabolite of nicotine, and these measures will help assess abstinence from cigarette smoking in response to our intervention. The additional follow-up visit details will be incorporated into the informed consent form and in the E-IRB application for IRB further review and approval.

